Brief Summary	
The primary objectives of this study are to examine the tolerability of pulsed low-intensity focused ultrasound (PLIFUS) and its effects on brain function measured via fMRI functional connectivity and symptom response in individuals with schizophrenia. A neuronavigated single-element piezoelectric device will be utilized to noninvasively deliver transcranial PLIFUS sonication to the right globus pallidus interna, a brain region implicated in schizophrenia. We aim to enroll participants with schizophrenia in a random order, sham-controlled crossover trial of a single session of PLIFUS counterbalanced with a single sham sonication session, one week apart until we reach 12 completers. After the participant provides written informed consent, a medical and psychiatric evaluation will be performed to determine eligibility for inclusion in the study. The next visit will involve a structural MRI to guide neuro-navigation. The first intervention visit will include a 10 minute PLIFUS sonication or sham sonication, preceded and followed by MRI brain scans and an exit medical examination. Psychiatric symptoms will be assessed immediately prior to sonication/sham, during sonication/sham, and 5 minutes, 30 minutes, 60 minutes, 1 day and 7 days after sonication/sham. The second intervention visit will consist of sonication or sham preceded and followed by MRI brain scans, in addition to symptom assessments and post-sonication/sham medical evaluation. Participants will be closely monitored during and after procedures for tolerability and adverse effects, including 1 and 7 day follow-up visits. The goal of this pilot study is to establish feasibility and tolerability and to determine whether the sonication procedure produces effects on the imaging biomarker and on symptoms prior to proceeding to therapeutic trials using repeated administration. If PLIFUS effects on fMRI and symptom ratings are not detected in the first 12 completers with good quality imaging data, the trial will be changed to 3 sessions of PLIFUS or sham administered over 5 days for 4 subsequent participants.

Phase	Phase 2

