Statistical Analysis	Because this is a pilot feasibility study, we will examine results after the first 12 participants with good quality imaging data who have completed both phases, and will either continue the study unchanged or, if no signal is detected by fMRI or symptom change, we will switch to administering 3 sessions of PLIFUS or sham over 5 days. We will define our threshold for signal detection as an effect size of 0.5 or greater for the comparison between treatment groups (PLIFUS or sham) of change of biomarkers (fMRI and symptom severity) from baseline to post-treatment. All results will be considered exploratory. Formal statistical analyses will be performed using standard methods for a random-over crossover design; safety outcomes will be descriptive.

Schematic of Study Design

1 Key Roles

[name]

Department of Psychiatry, NYU Langone Medical Center
[name]
[name]
[contact]
[contact]

[name] (Co-PI)

Department of Psychiatry, NYU Langone Medical Center
[name]
[name]
[contact]
[contact]

[name]

Department of Psychiatry, NYU Langone Medical Center
[name]
[name]
[contact]
[contact]

[name], Statistician

Department of Population Health, NYU Langone Health
[name]
[name]
[contact]
[contact]

F. [name]

Department of Child and Adolescent Psychiatry, NYU Langone Medical Center
[name]
[name]
[contact]
[contact]

2 Introduction, Background Information and Scientific Rationale

2.1 *Background Information and Relevant Literature*

2.1.1 **The Need for New Treatment Approaches in Schizophrenia**

Schizophrenia is a disabling chronic illness characterized by psychosis (delusions and hallucinations), negative symptoms (apathy and reduced emotional expression) and cognitive deficits. Antipsychotic medications, which block dopamine transmission, substantially improves delusions and hallucinations in approximately 60% of patients, but side effects are poorly tolerated and relapse is common ¹. Psychosis can be very distressing for patients and their families, often results in hospitalization, and may contribute to violence. Currently there is no effective treatment for negative symptoms and cognitive deficits.

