4.1 Description of Study Design

This is a single-site, phase 2, sham-controlled random-order cross-over pilot trial of PLIFUS targeting the right Gpi in individuals with schizophrenia. Twelve individuals with schizophrenia who report continuous hallucinations or delusions of moderate or greater severity will receive one session of PLIFUS and one session of sham PLIFUS in random order, one week apart. If no effect of PLIFUS is detected on measures of functional connectivity or psychotic symptoms in the first 12 completers with good quality imaging data, the trial will be changed to 3 sessions of PLIFUS or sham administered over 5 days for 4 subsequent participants.

Potential participants will be enrolled at NYU Langone Manhattan, NYU Langone Brooklyn, and Bellevue Hospital. Recruitment-only procedures will occur at Manhattan Psychiatric Center (see section 5.5.3). Following informed consent, potential participants will be screened by a psychiatrist who will assess psychiatric and medical status. A Brief Psychiatric Rating Scale will also be administered to assess inclusionary status. Individuals who meet inclusionary and exclusionary criteria will then have a structural MRI performed at the MRI visit and with each fMRI scan at Intervention Visits 1 and 2 to guide neuronavigation of PLIFUS. The two sessions of PLIFUS/Sham will occur in random order, one week apart. Randomization schedule will be done using Matlab. Participants will first have an fMRI for measurement of right Gpi functional connectivity, preceded and followed by symptom rating scales. PLIFUS/sham will then be administered over 10 minutes, during which symptom ratings will again be recorded. Symptom ratings will be repeated 5, 30, and 60 minutes, 1 day and 7 days post-sonication/sham. fMRI will be repeated starting 10 minutes after sonication/sham. Safety assessments will be completed prior to discharge of participants 1 hour after each sonication/sham session and after 24-48 hours and 7 days.

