4.2 Study Endpoints

4.2.1 Primary Study Endpoints

The primary study endpoint is the change in Gpi functional connectivity from baseline (pre-sonication) to post-sonication. The change in functional connectivity will be compared between PLIFUS and sham conditions. This measure was selected because of our prior finding that increased Gpi functional connectivity is highly correlated with psychosis severity in schizophrenia and because Fallon and colleagues ¹⁴ demonstrated that a single session of PLIFUS decreased functional connectivity in macaques.

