addition to all adverse events recorded by the SAFTEE assessments, the DSMB will receive a report of any additional participant complaints, instances of participant distress, or breaches of confidentiality. Because this is a pilot study with a very small sample size, formal statistical criteria are not identified in advance for a stopping rule. The DSMB may halt the study for reasons of safety—we are not aware of any significant safety concerns. The DSMB must approve the decision to switch from one session of PLIFUS to 3 sessions if no effect is detected after the first 12 completers with good quality imaging data. A failure to detect an effect size of 0.5 or greater compared to sham on the AHRS, DESA, and PSYRATS total score or on GPi functional connectivity after the first 12 participants will define “no effect” and trigger a switch to 3 treatment sessions over 5 days for phase II of the study which will involve an additional 4 participants. The DSMB will also be provided copies of all communications with the IRB. The DSMB will meet prior to initiation of the study and a minimum of every six months and will be provided data regarding enrollment and side effects and a study summary prior to each meeting. [name] and study staff will not attend the closed section of the DSMB meetings. Throughout the study, notification of any Serious Adverse Events (SAEs) as well as any proposed investigator-initiated changes in the protocol will be submitted to the DSMB. Based on its review of the revised protocol, the DSMB will identify the data parameters and format of the information to be regularly reported. All SAEs and adverse events will be tabulated and submitted to the IRB and DSMB in the bi-annual (every 6 months) data reports or at the time of continuing review. AEs will be reported to the IRB annually (at continuing review) if they are expected, related, and harmful. A summary of the outcomes of the safety reviews as prepared for the DSMB along with accumulated adverse events and deviations will be submitted to the IRB as part of an annual progress report at the time of the Continuing Review submission.

8 Clinical Monitoring

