A study psychiatrist will be present during all sessions of PLIFUS and sham. Participants will be monitored during and after sonication until psychiatrically cleared by the study psychiatrist 1 hour after completion of each session. Participants will be contacted 24-48 hours and 7 days after each treatment period and symptoms, side effects and suicidality assessed.

9 Statistical Considerations

This is a pilot study intended to obtain preliminary data to guide future studies. The analysis will primarily be descriptive for this purpose and, due to the small sample size, effect sizes will be the primary signal of target engagement. Consistent with other studies in the field, we have selected an effect size of 0.5 as our threshold. In addition, there is a pre-planned review of results after completion of the first 5 participants; the administration of PLIFUS/sham will be increased from one session to three sessions over 5 days if an effect size of 0.5 or greater with PLIFUS is not detected in change from baseline in GPi functional connectivity or symptom response compared to sham.

The primary statistical analysis will be performed in completers without imputation of missing data and will be change in primary outcomes (GPi functional connectivity and symptom severity) from baseline to the first measure post-sonication or sham (immediately post-sonication for symptoms; 10-30 minutes for fMRI). PLIFUS and sham PLIFUS will be compared using a linear mixed effects model with baseline measures (GPI functional connectivity and severity of psychotic symptoms) as continuous variables; treatment (PLIFUS or sham) and sequence as categorical variables; and participant as a random effect. Similar secondary exploratory analyses will be performed at additional time points (symptom severity during sonication, 60 minutes, 1 day and 7 days after sonication). Secondary analyses of other outcome measures (BPRS total score, PSYRATS and CGI) will be analyzed following the same approach. Safety measures, including the SAFTEE and C-SSRS will be summarized descriptively. If the study design is adapted (sonication increased to 3 sessions) after the first 12 completers with good quality imaging data, results from the first 12 completers and subsequent 4 participants will be analyzed separately.

Sample Size

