9.1 Measures to Minimize Bias

9.1.1 Enrollment/Randomization/Masking Procedures

Because this is a cross-over study, the primary concern with randomization imbalance is with an order effect. We will examine this possibility statistically. The sham condition consists of an identical procedure during which the sonication equipment produces an identical noise. We believe this will fully mask the treatment condition but will ask participants after each session which condition they believe they received and will analyze these results to verify the success of our masking.

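### The primary crossover model has no period term, so a visit-1/visit-2 difference in pre-to-post change stays in the effect size compared with 0.5

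*Combined protocol and SAP*

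**What the plan says.** Section 4.2.1 defines the outcome within each visit: "The primary study endpoint is the change in Gpi functional connectivity from baseline (pre-sonication) to post-sonication". Section 9 compares PLIFUS with sham in completers by a linear mixed model. Its terms are a continuous baseline, "treatment (PLIFUS or sham) and sequence as categorical variables; and participant as a random effect". No period or visit effect is listed.

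Section 9 makes effect sizes the main signal of target engagement and sets the threshold at 0.5. Section 7.15 attaches the consequence: "A failure to detect an effect size of 0.5 or greater compared to sham on the AHRS, DESA, and PSYRATS total score", or on GPi connectivity, counts as no effect and triggers the move to three sessions in four further participants.

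Three other statements bear on the point:
- The Protocol Summary says "Formal statistical analyses will be performed using standard methods for a random-over crossover design".
- Section 9.1.1 says "the primary concern with randomization imbalance is with an order effect. We will examine this possibility statistically".
- The Brief Summary describes "a single session of PLIFUS counterbalanced with a single sham sonication session, one week apart until we reach 12 completers", but on how the order is generated Section 4.1 says only "Randomization schedule will be done using Matlab".

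**The concern.** In a two-treatment, two-period crossover, sequence is a between-participant factor. It shifts a participant's overall level and drops out of the PLIFUS-minus-sham difference. Period is the treatment-by-sequence contrast, which the stated model leaves out.

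Because the outcome is change from the same visit's own baseline, a shift common to the pre and post measures largely cancels. What does not cancel is a visit difference in the change itself, for example if anxiety or expectancy makes the response to the first session differ from the response to the second. Section 2.1.5 itself names expectancy as a possible influence on the measures.

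With equal sequence groups, such a difference leaves the mean treatment contrast unbiased but inflates the SD of the paired differences. With unequal groups it also moves the contrast, up or down. Over repeated randomisations that movement averages to zero; in the one trial that is run it does not. An equal split is not assured, because the analysis set is completers and the switch rule uses those with good quality imaging. The review after five participants that Section 9 also mentions cannot be split equally at all.

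The estimate matters because Section 7.15 has the DSMB decide without statistical tests, so the observed effect size is itself the quantity judged.

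**Working it through.** The plan states no power, SD or period effect, so there is no figure to reproduce.

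**From the documents:** N = 12 completers (Section 9, Sample Size); threshold 0.5 (Sections 7.15 and 9); model terms as quoted.

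**Assumed:** the visit difference P, the sequence split, and the standardiser, which the plan does not name.

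**Set-up.** Let D be a participant's reduction under PLIFUS minus the reduction under sham, with mean τ and SD 1 within a sequence. Let P be the visit-2 minus visit-1 difference in reduction, in SDs of D. Let L participants receive PLIFUS at visit 2 and E at visit 1. D has mean τ + P in the first group and τ − P in the second.

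**Shift in the estimate without period:** P(L − E)/12.
- 6:6: 0.
- 7:5: ±P × 2/12 = ±0.04, ±0.08, ±0.17 for P = 0.25, 0.5, 1.0.
- 8:4: ±P × 4/12 = ±0.08, ±0.17, ±0.33.

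With period in the model, the estimate is the average of the two sequence-specific means of D, and P drops out at any split.

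**Effect size at 6:6, true effect 0.50, paired-difference SD.** Using the n − 1 divisor, 0.5/√(1 + P² × 12/11) = 0.484, 0.443, 0.346 for P = 0.25, 0.5, 1.0.

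**Same, standardised by the change-score SD** (within-person correlation 0.5 assumed): 0.5/√(1 + (P²/4) × 12/11) = 0.496, 0.484, 0.443.

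**Chance that one observed effect size reaches 0.5 when the true effect is 0.50** (200,000 simulated trials per setting, paired-difference SD). Where two figures appear, the first has the larger group receiving PLIFUS at the visit with the greater reduction, and the second is the reverse.

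| Split | P | Without period | With period |
|---|---|---|---|
| 6:6 | 0.25 | 0.493 | about 0.52 |
| 6:6 | 0.5 | 0.435 | about 0.52 |
| 6:6 | 1.0 | 0.254 | about 0.52 |
| 7:5 | 0.5 | 0.542 or 0.335 | about 0.52 |
| 8:4 | 0.25 | 0.602 or 0.389 | about 0.51 |
| 8:4 | 0.5 | 0.652 or 0.248 | about 0.51 |

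With a true effect of 0, split 8:4 and P = 0.5, the chance is 0.113 or 0.011 without period and about 0.067 with it.

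**Mixed-model check** (300 simulated trials, stated model with baseline, true effect 0, split 8:4, Monte Carlo SE about 0.02). A 1 SD level shift in both pre and post gives a mean estimate of 0.02, so level shifts do cancel. A shift in the change of 0.5 or 1 gives 0.15 or 0.34 without period, and −0.02 or 0.01 with it.

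**How often the split is unequal.** If allocation were simple randomisation (an assumption), Binomial(12, 0.5) gives 0.226 for 6:6 and 0.388 for 8:4 or worse. Effective counterbalancing would lower the second figure.

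**The case against.** The other side has several fair points.

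- **The word sequence is not defined.** If it means first versus second session, it already is the period term and only the wording is at fault. That is not its usual crossover meaning, and the edit below settles it either way.
- **No section says the 0.5 effect size comes from the mixed model.** This is true. But an effect size computed directly from the paired differences carries the same visit difference, so the fix has to name the source of the effect size as well as add the term.
- **The probabilities are for one outcome.** Section 7.15 covers several symptom scales and connectivity, so these are not switch probabilities. This limit stands.
- **The shrinkage at 6:6 depends on the standardiser.** With the change-score SD it is slight at P = 0.25 to 0.5. With the pre-sonication SD there would be none. This stands too, but the shift at unequal splits remains.
- **The size of P is entirely assumed.** At P = 0.25 and 6:6 the chance moves only from about 52% to 49%.
- **The plan partly covers the point.** It promises to examine an order effect and to use standard crossover methods. Examining an effect is not adjusting for it, and the specific list in Section 9 governs over the general phrase in the summary.
- **Stakes are low.** Results are exploratory, and a switch needs DSMB approval and adds four separately analysed participants.

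**Conclusion.** The concern holds. As written, nothing in the plan removes a visit difference in pre-to-post change from the effect size judged against 0.5. At 6:6 the harm is a diluted effect size, to a degree set by the standardiser. At 7:5 or 8:4 the estimate also shifts, in either direction. For an assumed visit difference of 0.5 SD, the chance that a true 0.50 reaches the threshold on one outcome moves from about 52% to 44% at 6:6, and to 25% or 65% at 8:4. These sizes rest on assumed period effects, splits and standardiser. The omission itself does not. It should be corrected, but given the exploratory aims it does not undermine the trial.

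**What to change.** In Section 9, add period (visit 1 or visit 2) as a categorical fixed effect beside own-visit baseline, treatment and sequence, keep participant random, and define sequence as the order group. State that the effect size compared with 0.5 is computed from the period-adjusted treatment estimate, and name its standardiser. If that is the SD of the paired difference, take it within sequence, as √2 times the model's residual SD.

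The cost is one model term and one degree of freedom, with no new data. If there is truly no period effect:
- The SE of the treatment difference stays at 1/√12 = 0.289 at 6:6. At 8:4 it rises to 0.5 × √(1/8 + 1/4) = 0.306.
- Two-sided power at an effect of 0.5 (noncentral t, 11 df without period and 10 with) falls from 35.3% to 34.7% at 6:6, and from 35.3% to 31.5% at 8:4.
- At a true effect of 0 and 8:4, the chance of reaching 0.5 on one outcome rises from about 5.6% to 6.7%.

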4.2.2 Secondary Study Endpoints

Secondary study endpoints are measures of clinical symptoms, which are assessed using the following scales: AHRS, DESA, BPRS, and PSYRATS. Safety assessments will consist of the Columbia Suicide Severity Rating Scale (C-SSRS), MoCA, and SAFTEE and addendum assessment for side effects.

5 Study Enrollment and Withdrawal

Participants will be individuals with a diagnosis of schizophrenia who report continuous psychotic symptoms (auditory hallucinations or delusions) of at least moderate severity. Participants may be taking antipsychotic

medication or be medication-free, must be free of unstable psychiatric or medical illness, cannot have suicidal ideation, or a history of violence or of suicidal behavior (attempts), cannot have epilepsy or be taking anticonvulsant medication and must have no contraindication to MRI or sonication, including metal implants.

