7.2.2 Screening Visit (Days -30 to -1)

- Complete quiz documenting the subject's understanding of study procedures, risks and alternatives.
- Complete Assessment of Capacity
- Obtain written informed consent.
- Complete Consent Checklist to document that informed consent procedures have been followed (i.e., Key Information Sheet provided, all questions were answered by study staff, consent given prior to any procedures being performed, etc.)
- Complete a medical and psychiatric evaluation by a study psychiatrist, including history and physical examination and recording of medications.
- Complete the Buss-Perry Violence Questionnaire by a research assistant
- Obtain urine sample for pregnancy test and urine toxic screen
- The psychiatrist will also complete a Structured Clinical Interview for DSM5 (SCID) to establish a diagnosis of schizophrenia or schizoaffective disorder and to assess exclusionary diagnoses, including substance use disorders
- The study psychiatrist will complete the Columbia Suicide Severity Rating Scale (C-SSRS), MoCA, and CGI.
- A research assistant will complete the Brief Psychiatric Rating Scale (BPRS) to determine whether the candidate meets symptom severity criteria.
- Determine eligibility based on inclusion/exclusion criteria

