7.2.4 Intervention Visits

Intervention Visit 1: (Day 0)

- Administer CGI, C-SSRS, SAFTEE, SAFTEE addendum, and PSYRATS
- Obtain structural MRI scan for fMRI registration (5 minutes)
- Obtain fMRI resting state scan (20 minutes)
- Administer AHRS and DESA prior to starting intervention
- Administer PLIFUS/sham over 10 minutes (re-administer AHRS and DESA at 5 minutes)
- Repeat AHRS and DESA immediately after PLIFUS/sham
- Obtain structural MRI scan for fMRI registration (5 minutes)
- Obtain fMRI resting state scan (20 minutes)
- AHRS and DESA repeated immediately after fMRI scan
- PSYRATS and CGI 60 minutes after PLIFUS/sham
- Psychiatric and medical assessment, including MoCA, SAFTEE, and SAFTEE addendum, 1 hour after PLIFUS/sham

Intervention Visit 1B: (Day 1-2) (may be remote)*

- AHRS and DESA
- SAFTEE & addendum
- C-SSRS

Intervention Visit 2 (Day 6-8)

- Administer CGI, C-SSRS, SAFTEE, SAFTEE addendum, and PSYRATS
- Obtain structural MRI scan for fMRI registration (5 minutes)
- Obtain fMRI resting state scan (20 minutes)
- Administer AHRS and DESA prior to starting intervention
- Administer PLIFUS/sham over 10 minutes (re-administer AHRS and DESA at 5 minutes)
- Repeat AHRS and DESA immediately after PLIFUS/sham
- Obtain structural MRI scan for fMRI registration (5 minutes)
- Obtain fMRI resting state scan (20 minutes)
- AHRS and DESA repeated immediately after fMRI scan
- PSYRATS and CGI 60 minutes after PLIFUS/sham
- Psychiatric and medical assessment, including MoCA, SAFTEE, and SAFTEE addendum, 1 hour after PLIFUS/sham

Intervention Visit 2B (Day 7-9) (may be remote)*:

- AHRS and DESA
- SAFTEE & addendum
- C-SSRS

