7.2.5 Final Study Visit (Day 14-16) (may be remote)*

- AHRS and DESA
- SAFTEE & addendum
- C-SSRS
- BPRS

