
17 Attachments

These documents are relevant to the protocol, but they are not considered part of the protocol. They are stored and modified separately. As such, modifications to these documents do not require protocol amendments.

- Device Manual attached

18 Schedule of Events

Activity	Screening Visit [Day -30 to -1]	MRI Visit [Day -30 to -1]	Intervention 1 [Day 0]	Intervention 2 [Day 7, 6-8]	Follow-up [Day 14, 13 to 15]
Study team procedures					
Consent	X				
Medical History	X				
Physical Exam	X				
Vital Signs	X				
Psychiatric History	X				
Psychiatric diagnosis (SCID)	X				
Demographics	X				
BPRS	X				X
PSYRATS			X	X	
BPAQ	X				
AHRS			X	X	
MoCA	X		X	X	
DESA			X	X	

CGI	X		X	X	
Experimental intervention					
Randomization		X			
PLIFUS or sham			X	X	
Safety Assessments					
SAFTEE & addendum			X	X	X
C-SSRS	X		X	X	X
Medical/psychiatric assessment			X	X	X
Imaging Assessments					
Structural MRI		X	X (pre and post-sonication)	X (pre and post-sonication)	
Resting state fMRI			X (pre and post-sonication)	X (pre and post-sonication)

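### BPRS total score is assigned to the PLIFUS-versus-sham crossover model but is rated only before both sessions and after both, so its treatment effect cannot be estimated

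*Combined protocol and SAP*

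**What the plan says.** Section 4.2.2 defines the secondary endpoints as clinical symptom measures, "which are assessed using the following scales: AHRS, DESA, BPRS, and PSYRATS".

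Section 9 describes the main analysis as change from baseline to the first measure after sonication or sham. The model has the baseline measure as a continuous covariate, "treatment (PLIFUS or sham) and sequence as categorical variables; and participant as a random effect". On the analysis set it says: "The primary statistical analysis will be performed in completers without imputation of missing data". It then extends this to the other scales: "Secondary analyses of other outcome measures (BPRS total score, PSYRATS and CGI) will be analyzed following the same approach".

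The visit lists give the timing:

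- **Screening (7.2.2, Day -30 to -1):** "A research assistant will complete the Brief Psychiatric Rating Scale (BPRS) to determine whether the candidate meets symptom severity criteria".
- **Intervention Visits 1 and 2 (7.2.4):** PSYRATS and CGI are given at the start of each visit and again afterwards ("PSYRATS and CGI 60 minutes after PLIFUS/sham"). BPRS is not listed at either visit, nor at Visits 1B and 2B.
- **Final Visit (7.2.5):** BPRS is listed.
- **Schedule of Events (Section 18):** BPRS is marked at Screening and Follow-up only.

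The Early Termination Visit (7.2.6) also lists BPRS, but Section 13.1 says that early terminators' data are not kept electronically.

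**The concern.** A crossover model of change needs, for each person, an outcome that belongs to PLIFUS and another that belongs to sham. The schedule provides neither for BPRS. The first rating precedes both sessions and the second follows both, so the single difference contains PLIFUS, sham, expectancy and the passage of time.

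The risk is that the analyst finds the model cannot be fitted and reports the Screening-to-Final change in its place. In a pilot that takes effect sizes as its main signal and is meant to support grant proposals, such a figure could be read as a PLIFUS effect.

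**Working it through.** The documents give no power, standard deviation or expected effect for BPRS, so there is no figure of the plan to reproduce. The question is whether the treatment term can be identified.

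**Inputs.** 12 completers (Section 9, Sample Size). Fixed effects: intercept, baseline, treatment, sequence (Section 9). Rating times as in 7.2.2, 7.2.4, 7.2.5 and Section 18. A 6:6 sequence split is assumed where a split is needed.

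**1. Scales rated in each period (PSYRATS, CGI).** Two change scores per person give 12 × 2 = 24 rows. The matrix has rank 4 of 4 and treatment is estimable. Adding a period term gives rank 5 of 5.

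**2. BPRS as scheduled.** Two ratings per person give one change score, so there are 12 rows. Treatment can be coded in two ways:

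- *By exposure.* Every completer has had both conditions by the Final Visit. The treatment column is constant and duplicates the intercept: rank 3 of 4.
- *By last treatment received*, relying on the 7-day lookback in 7.1.1. Everyone randomised to PLIFUS first has sham last, and the reverse. The treatment column is then the sequence column or its complement: rank 3 of 4.

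Both results hold for every split from 3:9 to 9:3, and they do not depend on sample size. With one row per person, the participant random effect also cannot be separated from residual error.

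**3. Fallback without sequence.** Final BPRS can be compared by last treatment. This is a between-person comparison, valid only without carryover from the first session. The 95% CI half-width in SD units is t(0.975, 10 df) × √(1/n₁ + 1/n₂):

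| Split | Half-width (SD) |
|---|---|
| 6:6 | 2.228 × √(1/6 + 1/6) = 1.29 |
| 5:7 | 1.30 |
| 4:8 | 1.36 |
| 3:9 | 1.49 |

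At 6:6 this is 1.29 / 0.5 = 2.6 times the plan's effect-size threshold.

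**4. Time covered by the one change score.** By 7.2.2 and 7.2.5 it spans 14 − (−1) = 15 to 16 − (−30) = 46 days. By the Schedule of Events it spans 13 − (−1) = 14 to 15 − (−30) = 45 days. Section 5.6 expects at most 21 days for the whole process. On any of these, both sessions fall inside the interval.

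**5. What extra ratings would allow.** Suppose BPRS were added at Visits 1 and 2, with a true effect δ. Ignore baseline adjustment and let period effects cancel over equal sequences.

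- *Two change scores sharing the Visit 2 rating.* If the effect washes out by the next rating, PLIFUS-first gives δ − (−δ) = 2δ and sham-first gives δ − 0 = δ, a mean of 1.5δ. If it fully persists, both give δ.
- *Post values (Visit 2 and Final) with the single Visit 1 baseline.* Under washout both sequences give δ. Under full persistence they give 0 and δ, a mean of 0.5δ.

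A simulation with baseline adjustment agrees with this pattern. The true effect was 1.0. Between-person SD 1–2 and error SD 0.5–1 were assumed, because the documents give no variances. Large-sample estimates for shared change scores were 1.24–1.46 under washout and 0.75–0.97 under persistence. For post values they were 0.99–1.00 and 0.50. The post-value model with treatment, period and sequence has 24 rows and rank 5 of 5.

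**The case against.** The strongest reply is that little depends on BPRS. The Protocol Summary calls all results exploratory and names only self-report hallucination and delusion scores as secondary endpoints. Section 9 says the analysis is mainly descriptive, and the no-effect rule in 7.15 uses AHRS, DESA, PSYRATS and connectivity. All of this stands and limits the impact. It does not make the term estimable, and both 4.2.2 and Section 9 commit to BPRS as an outcome.

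A second reply is that a Day 6–8 rating may simply have been left out of 7.2.4. The 7-day lookback would fit that, as would the statement in Section 8 that symptoms are assessed 7 days after each treatment period. This is possible, but the visit lists and the Schedule of Events agree that no such rating exists. Whichever was intended, Section 9 and the schedule do not match.

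The early-termination BPRS does not help, since the analysis is in completers.

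Two technical objections are fair. The fallback interval is for an analysis nobody plans, and with baseline in the model it would have 9 degrees of freedom (1.31 SD rather than 1.29). Also, the post-value model for added ratings is better only if the effect washes out; under full persistence it loses half the effect. Neither affects the main point.

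**Conclusion.** The concern holds. As scheduled, 0 of 12 completers supply a within-person PLIFUS-versus-sham contrast on BPRS, and the stated model has rank 3 of 4 under either coding of treatment. This follows from the rating times alone and needs no assumption about variances, effect size or allocation balance. Only the fallback interval and the simulated figures rest on assumptions.

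The defect is confined to BPRS. The fMRI contrast, the immediate AHRS and DESA contrasts, and the 60-minute PSYRATS and CGI contrasts are unaffected. It should be corrected because the stated analysis cannot be run, but no primary result or decision rule depends on it.

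**What to change.** **Main change.** In Section 9, remove BPRS total score from the sentence that extends the treatment-comparison model to other outcomes. State that its Screening-to-Final change will be reported descriptively, that it spans both conditions, and that it is not an estimate of a PLIFUS effect. The cost is one sentence and no new data.

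**Only if a BPRS treatment contrast is wanted.** Add BPRS at the start of Intervention Visits 1 and 2, which is two extra ratings per person (24 for 12 completers) at visits already staffed. Do not use the Visit 2 rating as both period-1 outcome and period-2 baseline in a change-score model. Model the Visit 2 and Final values on the single Visit 1 baseline, treatment, period and sequence, with a participant random effect. State two limits:

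- The model assumes no carryover, and a fully persisting effect would be halved.
- The 7-day lookback fits only approximately. Session 1 to Visit 2 is 6–8 days. Session 2 to Final is 14 − 8 = 6 to 16 − 6 = 10 days by 7.2.5, or 13 − 8 = 5 to 15 − 6 = 9 days by the Schedule of Events.

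**Side note.** While editing, reconcile the Final Visit window (Day 14–16 in 7.2.5, Day 13–15 in the Schedule of Events) and the overall span with the 21-day expectation in 5.6. Add the follow-up AHRS and DESA marks missing from the Schedule of Events.
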